## **Purpose:**

Primary purpose: To investigate whether intraoperatively administered morphine improves postoperative analgesia.

Secondary purpose: To investigate whether intraoperatively administered morphine increases opioid related adverse effects.

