## **PICO:**

Population: adult patients who have undergone elective laparoscopic cholecystectomy

Intervention: change in anesthesia technique to include an intraoperative dose of morphine

Comparison: A) no morphine = patients operated in the year before the change in anesthesia protocol (June 1st 2022 – May 31st 2023)

B) morphine = patients operated in the year following the change in anesthesia protocol (Jan 1st 2024 – Dec 31st 2024)

Outcomes: Primary: use of rescue analgesia in the postoperative ward

Secondary: pain scores on admittance and discharge from postoperative ward, time from end of surgery to admittance to postoperative ward (surrogate measure for emergence from anesthesia), use of rescue antiemetic treatment in the postoperative ward, time in postoperative ward, use of analgesic and antiemetic treatment in the first 24 hours after discharge from postoperative ward, time in hospital.

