### **Design:**

Retrospective, observational, data from patient records/register based

Investigation site: Hospital of South West Jutland Esbjerg

Population:

2 groups:

- a) No morphine intraoperatively: Patients operated in the year before change in anesthesia protocol
- b) Morphine intraoperatively: Patients operated in the year after change in anesthesia protocol

Inclusion criteria:

- Patient having undergone elective laparoscopic cholecystectomy

Exclusion criteria:

- Age under 21 (because these patients are admitted to a separate ward for children and young adults)
- Patients who are unable to give consent to anesthesia
- Patients who cannot participate in pain-scoring by numerical ranking scale (NRS)
- Patients with chronic pain (characterized by patient receiving regular analgesic treatment and patients with active or previous contact to pain clinic)
- Patients with active or previous substance abuse
- Emergency surgery

Outcomes

Primary:

- Use of rescue analgesia (calculation of total morphine equivalents) in the postoperative ward

Secondary:

- Intraoperative opioid use (calculation of total morphine equivalents)
- Time from end of operation to admittance to postoperative ward (surrogate measure of emergence from anesthesia)
- Pain score at admittance to postoperative ward, scale from 0 to 3\*
- Pain score at discharge from postoperative ward, scale from 0 to 3\*

\*Due to retrospective, register based design we cannot use standard numerical ranking scale (NRS), since local practice is to register pain in intervals of NRS: no pain = 0, light pain = 1-3, moderate pain = 4-6, severe pain = 7-10

- Use of rescue antiemetic treatment in the postoperative ward
- Time in postoperative ward
- Analgesic use in surgical ward during first 24 hours if admitted\*\*
- Use of antiemetic treatment in surgical ward during first 24 hours if admitted\*\*
  - \*\* It is expected that a large proportion of the included patients will be managed as outpatients.
- Total admission time.

Other data collected for statistical analysis:

- Age at operation
- Gender
- ASA-classification
- Co-morbidity
- Height
- Weight
- Smoking habits (smoker/non-smoker)
- Use of alcohol (none, 1-21 units per week, > 21 units per week)
- In-patient/out-patientstatus
- Anesthesia maintenance (intravenous or inhalational)'
- Dose of fentanyl, remifentanil and morphine
- Use of lidocaine
- Postoperative nausea and vomiting (PONV)-prophylaxis
- Use of vasopressor or inotropes

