- Paracetamol and/or NSAIDs given preoperatively or intraoperatively
- Pre- and postoperative C-reactive protein (CRP)-values, if taken

Analyses:

- Per protocol
  - o a) No-morphine vs b) Morphine
  - o T-test, statistical difference in:
    - Analgesic use in postoperative ward (primary)
    - Intraoperative analgesic use
    - Pain scores in postoperative ward
    - Time for end of surgery to admittance to postoperative ward

- Use of rescue antiemetic drugs in postoperative ward
- Time in postoperative ward
- Use of opioid analgesia and antiemetic drugs in surgical ward
- Time in hospital
- If necessary and possible logistic regression analyses.

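### The primary comparison of two calendar periods is fixed as an unadjusted t-test, while adjustment is optional, logistic and tied to no outcome

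*Protocol*

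**What the plan says.** The Purpose section sets a causal aim: "To investigate whether intraoperatively administered morphine improves postoperative analgesia". Under PICO, the comparison is between "patients operated in the year before the change in anesthesia protocol" (1 June 2022 to 31 May 2023) and "patients operated in the year following the change in anesthesia protocol" (1 January to 31 December 2024). The Design section calls the study retrospective and observational.

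The primary outcome under Design is a quantity: "Use of rescue analgesia (calculation of total morphine equivalents) in the postoperative ward". PICO words it more loosely as "use of rescue analgesia in the postoperative ward".

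The Analyses list at the end of the Design section opens with "T-test, statistical difference in", and its first item is "Analgesic use in postoperative ward (primary". Its last line is "If necessary and possible logistic regression analyses". No other regression, matching, weighting or stratification appears in the protocol.

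The Design section also lists further data to be collected for the statistical analysis. These include age, gender, ASA class, co-morbidity, height, weight, smoking, alcohol, type of anaesthesia maintenance, lidocaine, and paracetamol or NSAID use.

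**The concern.** Without randomisation, the difference in means between the two periods estimates the effect of morphine plus the effect of everything else that differed between them. Part of that is case mix, which the study records, but the one test fixed for the primary outcome uses none of it. The direction of any imbalance is unknown, so it could create an apparent benefit or hide a real one. A larger sample does not help: the bias stays the same while the standard error shrinks.

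The logistic clause does not close the gap, for two reasons.

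- **Wrong form.** Logistic regression does not directly model a morphine-equivalent total. It could serve a propensity score or a yes/no version of the outcome, but the protocol states neither use and gives no cut-off.
- **Conditional.** Adjustment is made only if judged necessary, with no criterion, so that decision can wait until the data have been seen.

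**Working it through.** **The two periods.** They last 365 and 366 days. The gap from 1 June to 31 December 2023 is 214 days. The start dates are 365 + 214 = 579 days apart, so the midpoints are 579.5 days (19 months) apart.

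**No figure to reproduce.** The protocol gives no sample size, SD, effect size or expected imbalance. Everything below rests on assumed inputs and shows only how the planned test behaves.

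**Assumptions.** Outcome SD 6 mg. Recorded patient characteristics explain a share R² of its variance. Their combined prognostic score shifts by d SD between periods. There are n patients per group.

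**Formulas.** Bias b = d × √R² × 6. Standard error SE = 6 × √(2/n). With no true effect, the two-sided 5% test rejects with probability 1 − Φ(1.96 − b/SE) + Φ(−1.96 − b/SE).

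Example with R² = 0.20, d = 0.3, n = 200: b = 0.3 × 0.447 × 6 = 0.805 mg; SE = 0.60 mg; b/SE = 1.34; rejection rate 0.269.

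| R² | d | b (mg) | n=100 | n=150 | n=200 | n=300 |
|---|---|---|---|---|---|---|
| 0.20 | 0.1 | 0.268 | 0.062 | 0.067 | 0.073 | 0.085 |
| 0.20 | 0.2 | 0.537 | 0.097 | 0.121 | 0.145 | 0.195 |
| 0.20 | 0.3 | 0.805 | 0.158 | 0.213 | 0.269 | 0.376 |
| 0.10 | 0.3 | 0.569 | 0.103 | 0.130 | 0.158 | 0.213 |

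With d = 0 the rate is 5% throughout.

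**Simulation** (3,000 runs per cell, six covariates, linear model with HC3 standard errors; R² = 0.20 and d = 0.3 unless stated):

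| Scenario | n=100 | n=150 | n=200 | n=300 |
|---|---|---|---|---|
| No effect: t-test | 0.154 | 0.216 | 0.271 | 0.379 |
| No effect: adjusted | 0.043 | 0.044 | 0.047 | 0.047 |
| No effect: adjusted, covariate reliability 0.7 | 0.052 | 0.063 | 0.065 | 0.079 |
| True −2 mg: t-test power | 0.288 | 0.391 | 0.523 | 0.669 |
| True −2 mg: adjusted power | 0.712 | 0.867 | 0.948 | 0.994 |

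- In the power rows the shift works against morphine: the t-test estimates −1.2 mg and the adjusted model −2.0 mg. A shift the other way would exaggerate the effect to about −2 − 0.8 = −2.8 mg.
- With reliability 0.7, a bias of 0.22 to 0.24 mg remains of 0.805 mg, so adjustment removes about 70% of it.
- For a skewed outcome with 40% zeros (d = 0.3; n = 100/200/300), the t-test rejects at 0.077/0.118/0.154 and the adjusted model at 0.038/0.055/0.049.
- With no imbalance, adjustment lowers the SE from 0.846 to 0.786 mg at n = 100 and from 0.490 to 0.444 mg at n = 300, a gain of 7% to 9%.

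**A second set of inputs** (one covariate with correlation 0.5 to the outcome, d = 0.3, n = 200) gave 32.9% for the t-test and 4.7% for the adjusted model.

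**The case against.** Covariate lists, model form and missing-data rules commonly belong in an SAP, which is not at hand, and the protocol plainly expects some adjustment because it collects covariates for that purpose. This holds for the detail. It does not hold for the core: the protocol names the primary test and the form of the optional regression, so an SAP that adjusted the primary comparison would have to replace that text, not complete it.

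The inputs are assumptions, and the design gives some reason to expect only modest imbalance: one site, elective patients only, the same exclusions in both groups, and two full years that balance season. At a 0.1 SD shift the false-positive rate is only 6% to 9%. Rescue opioid totals may well contain many zeros, and the skewed scenario then gives the milder rates. Both points stand. They limit the likely size, not the defect.

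If the t-test is read as fixed, the primary result is already determined, and the worry about choosing between two results after the fact loses force. That is fair. On a strict reading the primary result is settled but confounded; on a loose one it is open to choice. The confounding argument needs neither reading.

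Finally, change over calendar time and co-treatments introduced alongside morphine may matter more than case mix. This also stands: adjustment handles recorded differences only.

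**Conclusion.** The concern holds and should be fixed before analysis. The planned primary test cannot separate morphine from patient differences that the study itself records, and the only adjustment mentioned is conditional and does not directly model the primary outcome. Whether imbalance occurred, and in which direction, cannot be told from the protocol. On the assumed inputs, the false-positive rate runs from about 6% for a small shift to 38% for a 0.3 SD shift at 300 per group; a zero-heavy outcome gives 8% to 15% at the 0.3 SD shift. If the periods are balanced on these characteristics, the t-test is unbiased for that source and adjustment costs nothing in precision.

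**What to change.** **Primary analysis.** Prespecify a linear regression of the ward morphine-equivalent total on group with HC3 standard errors. Always adjust for age, gender, ASA class, co-morbidity, BMI (from height and weight), smoking and alcohol. Report the adjusted mean difference with its 95% CI and keep the unadjusted t-test as a companion.

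**Co-treatments.** Prespecify a second model that adds anaesthesia maintenance, lidocaine and pre- or intraoperative paracetamol/NSAID. Label it as the estimate of morphine apart from co-treatments. Tabulate their use by period, because the protocol speaks of a change in technique without saying which of them changed.

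**Variables to leave out.** Do not adjust for morphine dose, total intraoperative opioid (itself a listed outcome) or postoperative CRP. In-/out-patient status may be affected by treatment, so leave it out of the main model. Leave out preoperative CRP too, since it is recorded only when taken.

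**Other text.** Keep logistic regression for named yes/no outcomes. Add a sensitivity analysis comparing all eligible patients by period. State unmeasured change over time as a limitation.

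**Cost.** A few lines of text and no new data collection. Missing covariates need a stated rule, for example multiple imputation. The second model loses precision if a co-treatment moved with the protocol change: at 10% against 90% use, its SE rises by 1/√(1 − 0.8²) = 1.67. In simulation at 150 per group, with −2 mg for each of morphine and the co-treatment, the SE was 1.08 mg against 0.64 mg in the patient-only model, and power was 0.47. The patient-only model, however, estimated −3.60 mg for morphine in that case.

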**Anticipated time schedule:**

2023	Protocol, permissions and generation of data collection tool in Redcap
Feb - Sept 2024	Data collection, no-morphine group
Oct 2024 – April 2025	Data collection, morphine group
April 2025 - ?	Data management, analyses, manuscript, publication

**Ethics:**

Patients are all subject to standard anesthesia care as per the department guidelines (as per approved anesthesia protocol). No experimental drugs or techniques are used.

Written consent to access relevant patient files without direct consent from each patient as per the quality improvement nature of the study has been obtained.

We have consulted our local board of directors (approval date October 28th 2023, Acadre case no 23/47526) as well as the regional ethics committee (approval date July 3rd 2023, case no S-20232000-86).

**Perspective:**

Laparoscopic cholecystectomy is a frequent procedure. Despite wide attention to the problem, patients undergoing this procedure still experience considerable postoperative pain. We believe that our findings will improve knowledge in pain management and as such be of benefit to future patients

---

